21. **Treatment with investigational product PF-06863135:** Priming dose will be administered on C0D1. Maintenance dose will be administered on starting on C1D1. If a patient has received treatment with Q1W PF-06863135 for at least 6 months and disease assessments have remained stable over at least 2 months, consideration may be given to increasing dose intervals from weekly to every 2 or once every four weeks (once per cycle; only CXD1 dosing and activities applicable) weeks after consultation with sponsor. For every 2 week (Q2W) dosing, it would be preferable to skip dosing of PF-06863135 on days 8 and 22 of each cycle (ie, omit activities in gray columns). If the patient subsequently begins to have increase of disease burden, dose intervals should return to weekly dosing.
22. **Serum immunofixation electrophoresis (SIFE), serum protein electrophoresis (SPEP), serum free light chain analysis (FLC) tests and beta-2 microglobulin tests:** No need to repeat on C0D1 if baseline assessment performed within 3 days prior to that date. See Assessments [Section 7.2.1](#) for laboratory disease assessment tests list. Beta 2 microglobulin will be collected on C0D1 (other time points are optional). Note that SIFE will only be completed at baseline when electrophoresis shows no measurable protein, at suspected CR, and at suspected progression (clinical or biochemical). When a CR or a clinical or biochemical progression is suspected, SPEP, SIFE, and serum FLC tests will be repeated within 1 to 4 weeks. For patients scheduled to be dose escalated, samples will also be collected within 1 week prior to receiving the first higher dose. All samples will be collected prior to investigational

PF-06863135

C1071001

Final Protocol Amendment 9, 28 March 2023

| Schedule of Activities B Visit Identifier | Screening ¹ Days prior to enrollment | Treatment Period | | | | | | | | | | | | | | 1 month Follow-up ³⁵ | Survival Follow- up ³⁷ | | | |
|--|--|-------------------|---|--------------------------------|----|----|----|---------|----|----|----|-----------------|----|----|----|------------------------------------|---|-----------|-----------|-------|
| | | Priming Dose | | Maintenance Dose | | | | | | | | | | | | | | | | |
| | | Cycle 0 (1 wk) | | Cycle 1 (1 Cycle = 4 weeks) | | | | Cycle 2 | | | | Cycle 3 onwards | | | | EOT ³⁶ | | | | |
| Study Day | -28 to -1 | -14 to -1 | 1 | 2 | 1 | 2 | 8 | 15 | 22 | 1 | 8 | 15 | 22 | 1 | 8 | 15 | 22 | 28 d d | 90 d d | 120 d |

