- Blood sample for PF-06863135 blood level:** Approximately 5 mL sample of whole blood (to provide approximately 2 mL of serum) will be collected at each time point for PK analysis of PF-06863135. After Cycle 8, pre- and post-dose PK samples will be collected only on every 4th cycle (Cycle 8, Cycle 12, Cycle 16, etc.). An additional PK sample should also be taken if CRS is suspected or if the hospitalization period is extended beyond 24 hours on C0D1 or C1D1 for any reason, and a PK sample is not already scheduled to be taken.
- Anti-drug Antibodies (ADA) and Neutralizing Antibodies (Nab) against PF-06863135:** Collection of two 1 mL pre-dose serum samples (from 5 mL total whole blood) to detect the presence of antibodies to PF-06863135 is to be obtained prior to the start of treatment. Patients having an unresolved adverse event that is possibly related to anti-PF-06863135 antibodies at their last assessment will be asked to return to the clinic for ADA and drug concentration blood sampling at approximately 3-month intervals until the adverse event or its sequelae resolve or stabilize at a level acceptable to the investigator and sponsor. After Cycle 4, pre-dose ADA and Nab samples will be collected only on Cycles 6, 8, and every 4th cycle thereafter (Cycle 8, Cycle 12, Cycle 16, etc.).
- Soluble BCMA and other factors:** Approximately 3 mL sample of whole blood (to provide approximately 1 mL of plasma) will be collected at each time point for analysis of soluble BCMA and other factors by mass spectrometry. All 0 hour samples will be collected prior to investigational product administration on days whereby investigational product is to be administered. After Cycle 8, pre- and post-dose PK samples will be collected only on every 4th cycle (Cycle 8, Cycle 12, Cycle 16, etc.). An additional soluble BCMA/other factor sample should also be taken if CRS is suspected, and a sample is not already scheduled to be taken (eg. Cycle 3 onwards).
- Blood sample for lenalidomide and pomalidomide blood levels:** Approximately 3 mL sample of whole blood (to provide approximately 1.5 mL of plasma) will be collected into a 3 mL K2EDTA vacutainer tube at each time point within 2 hours prior to the administration of lenalidomide and pomalidomide, respectively, for PK analysis of lenalidomide and pomalidomide. Blood sample collection for lenalidomide and pomalidomide blood levels analysis will not be required for any patient transitioned to PF-06863135 monotherapy treatment.

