Details for PF-06863135 injections are provided in the current PF-06863135 IP Manual. The dose level will be assigned by the sponsor (see [Section 5.1 Allocation to Treatment](#)). For monotherapy Part 1, all patients should be weighed within 72 hours prior to Day 1 of each cycle to ensure they did not experience either a weight loss or gain >10% from the prior weight used to calculate the amount of PF-06863135 required for dose preparation. If the patient experienced either a weight loss or gain >10% compared to the prior weight used to calculate the initial dose or dose in the previous cycle, the amount of PF-06863135 required for preparation and administration for the current cycle must be recalculated using this most recent weight obtained. Should the institutional policy be such that the dose is required to be calculated if a patient experiences a weight gain of <10%, this will be allowed. Fixed-dosing approach will be applied in dose-finding for combination and also in all expansion parts of the study (See [Section 1.2.9.4](#)).

Each patient may receive PF-06863135 until disease progression, unacceptable toxicity, withdrawal of consent, patient no longer willing to participate in trial, or study termination. If a patient has received treatment with Q1W PF-06863135 for at least 6 months, and disease assessments have remained stable over at least 2 months, consideration may be given to increasing dose intervals from weekly to every 2 weeks or once per cycle (only CXD1 dosing and activities applicable) after consultation with sponsor. Cycles would remain the same length with any skipped weekly doses noted. If the patient subsequently begins to have increase of disease burden, dose intervals should return to weekly dosing.

For Parts 1C, 1D, 1E and Part 2 dose expansion: PF-06863135 will be administered as described for monotherapy PF-06863135, and each cycle will be 4 weeks in duration. On C1D1 for all patients and C0D1 for patients receiving a priming dose, PF-06863135 will be administered on an inpatient basis. On all other days, PF-06863135 will be administered on an outpatient basis.

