If a patient has received treatment with Q1W PF-06863135 for at least 6 months, and disease assessments have remained stable over at least 2 months, consideration may be given to increasing dose intervals from weekly to every 2 weeks or once per cycle (only CXD1 dosing and activities applicable) after consultation with sponsor. Cycles would remain the same length with any skipped weekly doses noted. For every 2 week dosing, it would be preferable to skip dosing of PF-06863135 on days 8 and 22 of each cycle. If the patient subsequently begins to have increase of disease burden, dose intervals should return to weekly dosing.

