R_{ac}	Observed accumulation ratio	$AUC_{cycle\ 2,\ \tau}/ AUC_{cycle\ 1,\ \tau}$

For patients enrolled in Part 2A, 2B 2C, and 2D of the study, trough PF-06863135 concentrations will be summarized descriptively by cycle.

Drug concentrations of lenalidomide (Parts 1C and 2C only), and pomalidomide (Parts 1D and 2D only) will be measured using validated methods and summarized by descriptive statistics (n, mean, standard deviation, coefficient of variation, median, minimum, maximum, and geometric mean) according to dosing cohort and time for each part of the study. No PK parameters will be determined for lenalidomide, or pomalidomide.

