8.2.5.2. Pharmacokinetic Concentrations

To assess the PK profile of PF-06863135, PK concentrations will be listed; summarized (n, mean, standard deviation, coefficient of variation, median, minimum, maximum, and geometric mean) by dose, cycle, day and nominal time; and plotted for subjects in the PK analysis set (as defined in [Section 5](#)), where missing and BLQ values will be handled as detailed in [Section 7](#) above.

Presentations for PF-06863135 time-concentration data will include:

- A listing of all concentrations sorted by dose, subject ID, period and nominal time post-dose. The listing of concentrations will include the actual sample collection times, and the time of dosing. Deviations from the nominal time will be given in a separate listing.
- A summary of concentrations by dose and nominal time post-dose, where the set of statistics will include n, mean, median, standard deviation, coefficient of variation (cv), minimum, maximum and the number of concentrations above the lower limit of quantification.
- Median concentrations against nominal time post-dose by dose (based on the summary of concentrations by dose and time post-dose), with all doses presented on the same plot.

Two plots will be generated, so that the concentrations can be presented on linear and logarithmic scales.

For summary statistics and median plots by sampling time, the nominal PK sampling time will be used.

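### Part 2 trough concentrations are summarised by cycle with no split by current dosing interval, so from about Cycle 8 the summaries can mix 7- and 14-day troughs

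*SAP*

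**What the plan says.** **Summary rule.** SAP 6.3 states for Part 2 that "trough PF-06863135 concentrations will be summarized descriptively by cycle", and Protocol 9.5.1 has the same rule. SAP 8.2.5.2 groups PF-06863135 concentrations in general "by dose, cycle, day and nominal time". Dosing interval is not a grouping factor in any of the three.

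**Permitted change of interval.** Protocol 5.4.2 sets the entry condition, "If a patient has received treatment with Q1W PF-06863135 for at least 6 months", together with disease assessments stable over at least 2 months. In that case "consideration may be given to increasing dose intervals from weekly to every 2 weeks or once per cycle", after consultation with the sponsor. Cycle length does not change: for Part 2 "each cycle will be 4 weeks in duration". For 2-weekly dosing, Schedule of Activities B (footnote 21) says "it would be preferable to skip dosing of PF-06863135 on days 8 and 22 of each cycle". No change in the amount given per dose is stated.

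**Late sampling.** Footnote 2 of the pharmacokinetic schedule B says "After Cycle 8, pre- and post-dose PK samples will be collected only on every 4th cycle". Late anti-drug antibody (ADA) samples follow the same pattern (footnote on ADA, same schedule).

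**The concern.** After a switch, the Day 1 pre-dose sample has the same dose, cycle, day and nominal time as before. It is now a 14-day trough, or a 28-day trough on once-per-cycle dosing, where it used to be a 7-day trough. None of the planned grouping factors can tell these samples apart.

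Two other SAP rules might have separated them but do not:

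- SAP 7.1.2 sets a concentration to missing for a worrying sampling-time deviation or an anomalous value. A pre-dose sample after a sponsor-agreed interval change is neither.
- SAP 8.2.5.1 mentions regimen, but only for the plots of dose-normalised AUC over the dosing interval and Cmax.

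The by-cycle table could therefore show troughs falling, and variability rising, because of the schedule. SAP 6.4.1 and 8.2.5.5 plan to explore the effect of immunogenicity on PK, and late ADA and PK samples share the same cycles. A fall due to the schedule could be misread there as an ADA effect, or elsewhere as clearance that changes over time.

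**Working it through.** **Inputs**

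- Projected half-life: 3.5 days (Protocol 1.2.9.1), 4-8 days (1.2.9.5), 10 days (1.2.3). These projections differ, so results are given across the range.
- Intervals: 7, 14 and 28 days.
- Share of patients who switch: not given. 40% is assumed for illustration, with 25%, 50% and 75% as a range.
- Model: one compartment, linear, steady state, unchanged dose.

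**1. Check of the model.** Protocol 1.2.9.1 projects an accumulation ratio below 1.33 for weekly dosing at a 3.5-day half-life. With k = ln 2 / half-life, the ratio is 1/(1 − exp(−7k)) = 1/(1 − 0.25) = 1.333. The model agrees with the protocol's figure.

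**2. Trough ratios.** The steady-state trough is proportional to 1/(exp(kτ) − 1). Hence:

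- 2-weekly / weekly = 1/(exp(7k) + 1)
- 28-day / weekly = (exp(7k) − 1)/(exp(28k) − 1)

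| Half-life (days) | 2-weekly / weekly | 28-day / weekly |
|---|---|---|
| 3.5 | 20% | 1.2% |
| 4 | 23% | 1.9% |
| 8 | 35% | 8.1% |
| 10 | 38% | 10.5% |

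With slow subcutaneous absorption (assumed rate 0.25 per day) the ranges are 29-42% and 2.5-12%. The first 14-day trough after a switch, before the new steady state, is exp(−7k) of the weekly value: 25-62%.

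**3. When mixing can begin.** Six months is 6 × 30.4375 / 28 = 6.5 cycles, so Day 1 troughs through Cycle 7 are unaffected. Affected samples are Cycle 8, then Cycles 12, 16 and later.

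**4. When 28-day troughs can enter.** Amendment 8 (06 June 2021) already records enrolment as complete. Once-per-cycle dosing came with Amendment 9 (28 March 2023), 660 days later. Taking off the 7-day priming cycle, 653 / 28 = 23.3 cycles. If the last patient's first dose was no later than Amendment 8, a patient without dose delays was already in Cycle 24 when the option appeared.

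**5. Effect on a cycle mean.** The pooled mean relative to the weekly mean is (1 − s) + s × ratio, where s is the share switched to 2-weekly dosing.

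- s = 40%: 0.6 + 0.4 × 0.20 = 0.68, and 0.6 + 0.4 × 0.38 = 0.75. The fall is 25-32%.
- s = 25%, 50%, 75%: the pooled mean is 80-85%, 60-69% and 40-54% of the weekly mean.

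**6. Comparison with average exposure.** At an unchanged dose, average concentration halves on 2-weekly dosing. At s = 40% the group average falls to 0.6 + 0.4 × 0.5 = 0.80, a fall of 20%, against 25-32% for the mean trough.

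**The case against.** **The table reports troughs that patients really had.** Exposure does fall when the same dose is given less often. This stands, and the by-cycle summary is not false. But the trough falls more than average exposure, and the table gives no sign that the schedule is the cause.

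**The information is recoverable.** Switches need sponsor consultation, skipped doses are noted (Protocol 5.4.2), and the SAP 8.2.5.2 listing carries actual sample and dosing times. This also stands. It makes the fix cheap, but no planned summary uses the information.

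**Few data are involved.** At the June 2022 cutoff Part 2 had 15 patients, all in Part 2A (Protocol 1.2.3.1). PK is a secondary objective, SAP 8.1 calls the summaries non-inferential, and the exploration of ADA on PK is conditional on the data. All of this limits the weight of the point.

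**Medians are planned too.** If 40% had switched and all their troughs lay below the weekly ones, the overall median would still be a weekly-dosing value. It would be a low one, at the (0.5 − 0.4)/0.6 = 17th percentile of the weekly patients.

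**Two stronger readings are tempting, and the documents do not support them.**

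- A reader might infer that once-per-cycle dosing distorts late cycles generally. With 40% on it, the mean would fall by 36-40% (0.6 + 0.4 × 0.105 = 0.64; 0.6 + 0.4 × 0.012 = 0.60). The amendment dates rule this out for Cycles 8 to 20.
- A reader might infer that the relation between exposure and response would point the wrong way, because stable disease is a condition for switching. No planned analysis relates by-cycle troughs to response. Exposure modelling is optional and may be reported separately (Protocol 9.5.3, SAP 8.2.5.4). The exposure-efficacy work in Protocol 3.4 used average steady-state concentration.

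**Conclusion.** The gap is real and its consequence is minor. From about Cycle 8 the planned Part 2 trough summaries can pool 7- and 14-day troughs under one label, and from about Cycle 24 they can also include 28-day troughs.

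For a patient who switches, the direction is clear: at steady state the trough drops by 62-80% on 2-weekly dosing and by 90-99% on once-per-cycle dosing, with no change in clearance. The effect on a cycle mean depends on the share switching, which the documents do not give; the 25-32% fall is illustrative.

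The figures rest on linear kinetics, an unchanged dose, steady state and the protocol's projected half-lives. The Cycle 24 limit rests on the dates of Amendments 8 and 9 and on the absence of dose delays. The SAP is written to the June 2021 protocol, so the 28-day case arises only under the current protocol, whose section 9.5.1 keeps the same by-cycle rule.

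**What to change.** In SAP 6.3 and 8.2.5.2, and for consistency in Protocol 9.5.1:

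- Limit the main by-cycle trough table to samples taken while the patient is on weekly dosing, meaning about 7 days after the previous dose, derived from actual dosing dates.
- Show post-switch troughs separately by current interval (every 2 weeks, once per cycle), and list them where cells are small.
- Use the same split in any exploration of ADA effect on PK.

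The cost is a few sentences and one grouping variable derived from dates already recorded. No new data are needed. The downside is small cells in late cycles, which listing handles.

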6.4. PD/Biomarker Endpoints

The biomarker endpoints will be used to help understand the in mechanism of action as well as potential mechanisms of resistance of PF-06863135 either as a monotherapy or in combination therapy.

Table 3. Biomarker Assays and Sample Sources

Biomarker	Matrix	Assay
Soluble immune factors	Serum	Immunoassay
Soluble BCMA/related factors	Plasma	Mass spectrometry
BCMA expression	BM aspirate	Flow cytometry
	BM biopsy	IHC
TBNK	Whole blood	Flow cytometry
	BM aspirate	Flow cytometry
Immune cell phenotyping	Whole blood	Flow Cytometry
	BM aspirate	Flow Cytometry

Table 3. Biomarker Assays and Sample Sources

Biomarker	Matrix	Assay
	BM biopsy (possible)	IHC
RNA profiling	Whole blood	RNA Sequencing
	BM aspirate and/or biopsy (possible)	RNA Sequencing
T cell repertoire analysis	Whole blood	DNA Sequencing
	BM aspirate and/or	DNA Sequencing
	Biopsy (possible)	

Abbreviations: BCMA = B-cell maturation antigen; BM = bone marrow; deoxyribonucleic acid = DNA; T, B, and NK cells = TBNK

- BCMA expression and enumeration of CD138+ benign and malignant plasma cell populations in bone marrow pre- and post-dose, as assessed by multiparameter flow cytometry;
- Pre- and post-dose levels of soluble BCMA;
- Enumeration of T, B, and NK subtypes in whole blood;
- T cell immunophenotyping, including but not limited to proliferation and activation markers in whole blood and bone marrow by flow cytometry analysis;
- The relative expression of RNA transcripts, including but not limited to, those associated with immune activation and immune regulation in bone marrow and peripheral blood;
- The abundance and diversity of T cell clones in bone marrow and peripheral blood;
 - BCMA expression on plasma cells and their spatial relationship to T cells by immunohistochemistry.
 - Collection of banked biospecimens unless prohibited by local regulations or ethics committee decision. Additional information on collection and potential use is provided in the Banked Biospecimens Section 7.7 Protocol C1071001.

6.4.1. Immunogenicity Endpoints

For the immunogenicity data, the percentage of subjects with positive ADA of PF-06863135 and Nab each will be further characterized in terms of antibody specificity and summarized by dose level (Part 1) or by treatment arms. For subjects with positive ADA or Nab, categorization as treatment-emergent or treatment-boosted, the magnitude (titer), time of onset, and duration of ADA or Nab response will also be described, if data permit. Potential impact of immunogenicity on PK and clinical response including PD markers, safety/tolerability and efficacy of PF-06863135 will be explored, if warranted by the data).

6.4.2. Outcomes Research Endpoints

Not applicable

6.5. Covariates

The analyses of the MTD do not use covariates, and none will be defined. There are no planned comparisons between dose groups.

7. HANDLING OF MISSING VALUES

Missing data will be excluded from the tabular summaries.

7.1. Pharmacokinetics

7.1.1. Concentrations Below the Limit of Quantification

In all data presentations (except listings), concentrations below the limit of quantification (BLQ) will be set to zero. (In listings BLQ values will be reported as “<LLQ”, where LLQ will be replaced with the value for the lower limit of quantification).

7.1.2. Deviations, Missing Concentrations and Anomalous Values

In summary tables and plots of the median values at each time point, statistics will be calculated having set concentrations to missing if 1 of the following cases is true:

1. A concentration has been collected as ND (i.e., not done) or NS (i.e., no sample),
2. A deviation in sampling time is of sufficient concern or a concentration has been flagged anomalous by the pharmacokineticist.

Note that summary statistics will not be presented at a particular time point if more than 50% of the data are missing.

7.1.3. Pharmacokinetic Parameters

Actual PK sampling times will be used in the derivation of PK parameters.

If a PK parameter cannot be derived from a subject's concentration data, the parameter will be coded as NC (i.e., not calculated). (Note that NC values will not be generated beyond the day that a subject discontinues).

In summary tables, statistics will be calculated by setting NC values to missing; and statistics will be presented for a particular dose with ≥ 3 evaluable measurements.

8. STATISTICAL METHODOLOGY AND STATISTICAL ANALYSES

Overview of analysis:

- Continuous data will be summarized using descriptive statistics (mean, median, SD, minimum, maximum, and 2-sided 95% CI where applicable)
- Categorical data (including point estimates) will be summarized by frequency counts, percentages and binomial 95% CIs using the Clopper-Pearson⁵ method.
- Kaplan-Meier estimates (product-limit estimates) will be presented and displayed graphically where appropriate, together with a summary of associated statistics (including 2-sided 95% CIs using log(-log) method according to Kalbfleisch and Prentice⁸).

8.1. Statistical Methods

The statistical summaries are non-inferential. The data are summarized by cohort defined by the initial dose, and route of administration of the study drug.

8.1.1. Analyses for Continuous Data

Continuous data will be summarized with the mean, median, minimum, maximum and standard deviation.

8.1.2. Analyses for Categorical Data

Categorical data will be summarized by number of unique subject incidence.

8.1.3. Analyses for Binary Endpoints

Binary data will be summarized using number of unique subject incidence, and Wilson's confidence interval for binomial proportions will be presented

8.1.4. Analyses for Time-to-event Data

The median, percentiles, and probabilities at particular points in time are estimated using the method of Kaplan and Meier. Kaplan-Meier estimates (product-limit estimates) will be presented and displayed graphically where appropriate, together with a summary of associated statistics including the median PFS time with 2-sided 95% CIs. The CIs for the median will be calculated according to Brookmeyer and Crowley, 1982.⁶

